4.3 Informed consent of the in-patient

The process of obtaining informed consent will be conducted in compliance with the principles of good clinical practice and within the rules set down by the approving Research Ethics Committee. Prior to consenting to the study, each participant will be provided with a full written and verbal explanation, and sufficient time will be given for full consideration. Any queries they have will be answered. The participant will then, if they agree, sign the consent form and a copy of this given to them. At any time, the participant may withdraw from the study without prejudice or without effect on their treatment.

4.3.1 Informed consent of the out-patient

In relation to patients seen in out-patients who are eligible; the study will be discussed verbally with them and documentation provided. They will be asked at that time to give their consent, and they will be asked again on day of surgery.

4.4 Randomisation

As this is a multicentre trial and considering the myriad of factors impacting healing after toe amputation, randomisation by minimisation will be generated centrally by third-party computer software (Sealed Envelope) to ensure equal distribution of patients in each cohort across the sites. Patients will be randomised in a 1:1 ratio. On the day of surgery, a nominated, independent member of the surgical team will access the randomisation software and show the operating surgeon. Of note, randomisation will be per patient and not per toe amputation; as such, a single patient undergoing two or more toe amputations simultaneously will only be randomised once.

4.5 Baseline patient data

Patients will have a full medical history taken and clinical examination as part of their standard care. The following will be recorded:

1. Weight;
2. Height;
3. Blood pressure;
4. Heart rate;
5. ECG findings;
6. Gender;

7. Ethnicity;
8. Date of birth;
9. Diabetes mellitus and glycaemic control, defined as the most recent HbA1c;
10. Insulin requirement for diabetic patients;
11. Hypercholesterolaemia;
12. Hypertension;
13. Previous myocardial infarction;
14. Previous coronary revascularisation;
15. Previous stroke;
16. Atrial fibrillation;
17. Peripheral arterial disease;
18. Smoking history;
19. Recent ipsilateral lower limb re-vascularisation;
20. ABPI +/- TPI in the index limb;
21. Chronic kidney disease, as defined by eGFR;
22. Baseline bloods at hospital admission, including white cell count, neutrophil count, haemoglobin, mean corpuscle volume, CRP, creatinine and urea, albumin, total protein
23. Baseline x-ray findings, including degree of osteomyelitis, osteopenia and soft tissue gas

5. Interventions

All procedures will be carried out by a vascular consultant or trainee with significant experience in the procedure. This will be a transmetatarsal amputation performed using either a bone cutter or a bone saw. The aim is for a successful healing of the wound, and no further re-interventions or re admission within a year. All patients will receive saline wound lavage. Wounds with extensive contamination will receive washout with 50% hydrogen peroxide solution. The most proximal specimen of bony resection will be sent for culture and sensitivity to the microbiology laboratory. The use of a drain and closure material are left to the discretion of the operating surgeon.

Continuation of antibiotics will be as per local microbiology guidelines and cultures and sensitivities will be followed. Patients will be followed up with x-ray within 48 hours of surgery to assess for bony fragments. Use of VAC or wound adjuncts will be documented.

6. Schedule of Events:

6.1 Follow up

All patients will be followed up with an x-ray at 6 months post-operatively to assess for bony healing, as is common practice in orthopaedic surgery. Any recurrence of symptoms, post-operative complications or concerns will be recorded. As per usual vascular practice, patients will be followed up in the community post-discharge and receive regular wound care from public health nurses. In order to determine approximate time from surgery to wound healing, sequential wound pictures will be sent on a fortnightly basis by the PHN to a secure HSE email account used by the trial investigators.

6.2 Withdrawals during follow up

At any time, the participant may withdraw from the trial with no bearing on any further management or intervention. The investigators may decide to remove anyone at any time if this is in the best interest of the patient.

6.3 Loss to follow-up

Any loss to follow up will be documented and explained to the best ability of the investigator. During consent, the importance of follow-up will be impressed upon, and any non-attendance to clinic or imaging will be followed up by a member of the team and the patient will be encouraged to attend if possible. Any reasons not able to attend will be recorded.

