3.2 Endpoints

3.2.1 Primary Efficacy Endpoint

The primary efficacy endpoint will be the number of patients in each group who underwent surgical reintervention at twelve months post-operatively.

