6.4 Protocol Violations

The following will be deemed a protocol violation and the participant will be removed from the trial:

1. Non-adherence to repeat imaging;
2. Withdrawal of consent for procedure or inclusion in study.

	Screening	Enrolment	Intervention	Follow up 6 weeks	Follow op 6 months	Follow up 1 year
Consent		X				
History and Exam	x	X				
Imaging	x		x		x	x
Intervention			x	x	x	x
Clinical follow-up				x	x	x

7. Safety Parameters:

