7.4 Event Reporting

All adverse events will be reported directly to the either the site or principal investigator. Recurrent adverse events or serious adverse events in isolation will be reported in turn to the local Ethical Committee and the risk assessment department for risk analysis.

8. Statistical considerations:

Post intervention, all patient outcomes will be recorded and assessed on intention to treat basis. We expect a certain degree of crossover from the bone cutter trial arm to bone saw trial arm, as is reflected in daily surgical practice. Furthermore, we expect a small number of patients may ultimately not undergo treatment as initially planned. Any losses to follow up will be reported. There are no studies investigating this particular trial question, as such there is no data on which to base a power calculation. For this pilot trial, we aim to recruit 20 patients into each arm i.e. 40 patients in total. All analyses will be performed on an intention to treat basis. The statistical analysis will be blinded. Binary outcomes will be analysed using the Chi-Square test. Non-parametric continuous variables will be compared using Mann-Whitney U Test. The time between surgery and measurable endpoints will be compared using Kaplan-Meier Survival Curves.

9. Ethical Considerations:

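### Twelve-month reintervention status is not retrieved for patients who stop attending, and sections 6.4 and 8 conflict on whether they stay in the primary analysis

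*Combined protocol and SAP*

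**What the plan says.** - **Endpoint (section 3.2.1).** The primary efficacy endpoint is "the number of patients in each group who underwent surgical reintervention at twelve months post-operatively". No denominator is given, and there is no rule for death or for unknown status.
- **Non-attenders (section 6.3).** "Any loss to follow up will be documented and explained to the best ability of the investigator". On missed visits, "any non-attendance to clinic or imaging will be followed up by a member of the team and the patient will be encouraged to attend if" they can. The section closes with one more step: "Any reasons not able to attend will be recorded". Nothing is said about finding out reintervention or vital status by another route.
- **Removal (section 6.4).** "The following will be deemed a protocol violation and the participant will be removed from the trial". The list that follows has two items: not adhering to repeat imaging, and withdrawing consent. The schedule table places follow-up imaging at 6 months and 1 year.
- **Analysis (section 8).** All analyses are by intention to treat. "Any losses to follow up will be reported". "Binary outcomes will be analysed using the Chi-Square test". Times to endpoints are to be compared with Kaplan-Meier curves, but no censoring rule is given and the curves are not tied to the primary endpoint.
- **Death.** It appears only in the definition of a serious adverse event (section 7.3).
- **Purpose (section 2.1).** The pilot exists to supply data for an accurate power calculation for a later trial.

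**The concern.** Reintervention is a hospital event. Theatre and admission records can show it whether or not the patient comes to clinic or has an x-ray. The plan nevertheless responds to non-attendance only by urging attendance and noting why it failed. A patient who stops attending and is re-operated on in month 8 may therefore have an outcome that could be known but is not collected.

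The plan then gives two incompatible signals about that patient. Section 6.4 takes out anyone who misses repeat imaging; section 8 keeps everyone as randomised. Neither says what value an unknown outcome takes.

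The 12-month rate is the main figure that the pilot hands to the next trial. Each patient is 5 percentage points of an arm of 20, so a handful of unresolved patients can move the rate materially. The protocol's introduction names renal disease, arterial disease and concurrent sepsis as risk factors for amputation failure. If such patients are also more likely to stop attending, which is plausible but not documented, the unknown outcomes are not a random subset.

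**Working it through.** **No stated figure to reproduce.** Section 8 sets 20 per arm (2 × 20 = 40) and says that there are no data for a power calculation. It gives no event rate, effect size, alpha or loss rate. The numbers below are illustrations.

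**Inputs**
- 20 per arm: section 8.
- 43%: the cited Irish cohort in the introduction, 63/146 = 43.2%. This is ipsilateral re-amputation with no 12-month horizon stated, so using it for this endpoint is an assumption. It is taken as the rate p among patients whose status is known.
- Fraction d of an arm lost early with status unknown: assumed at 10%, 20% and 30%. Deaths are not included in d.

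**Step 1. What each reading of the plan yields**

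With n = 20, observed events are p × n(1 − d).
- Counted as event-free, over all randomised: p(1 − d)
- Removed (section 6.4): p
- All counted as events: p(1 − d) + d

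For d = 20%, 4 are lost, 16 are observed, and expected events are 0.43 × 16 = 6.88. The three results are 6.88/20 = 34.4%, 6.88/16 = 43% and (6.88 + 4)/20 = 54.4%.

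| Lost per arm | Event-free | Removed | All events |
|---|---|---|---|
| 2 (10%) | 38.7% | 43% | 48.7% |
| 4 (20%) | 34.4% | 43% | 54.4% |
| 6 (30%) | 30.1% | 43% | 60.1% |

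The outer columns also bound the rate over all randomised patients. The gap between them always equals d, so only retrieving the outcomes narrows it. The middle column equals the rate in all randomised patients only if those lost resemble those observed.

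**Step 2. Effect on the future trial**

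Assume a 30% relative reduction, two-sided 5%, 80% power and 1:1 allocation. With p2 = 0.7 × p1 and p̄ their mean, n per arm = [1.96√(2p̄(1 − p̄)) + 0.84√(p1(1 − p1) + p2(1 − p2))]² / (p1 − p2)².
- p1 = 34.4%: 304 per arm, 608 in total
- p1 = 43%: 218 per arm, 436 in total
- p1 = 54.4%: 146 per arm, 292 in total

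The same pilot data could thus support a planned total anywhere from 292 to 608.

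**Step 3. Unequal loss**

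Take equal 43% rates, with 1 of 20 lost in one arm and 4 of 20 in the other. If the lost are counted as event-free, the arms show 0.43 × 19/20 = 40.9% and 0.43 × 16/20 = 34.4%, an artificial gap of about 6.5 points. Removal that is unrelated to outcome produces no such gap.

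**Step 4. Deaths**

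A death before reintervention, with status known, is a non-event that stays in the denominator. Cumulative incidence with death as a competing event treats it the same way. Death therefore does not bias that quantity downward and belongs apart from loss. Censoring deaths in a Kaplan-Meier curve would instead overstate the incidence of reintervention.

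**The case against.** **The plan never says that lost patients are event-free.** A reader might infer from a bare count and intention to treat that patients who die or stop attending are scored as free of reintervention, so that the rate is biased downward. The documents do not support that. No section assigns such patients an outcome, and section 6.4 would take many non-attenders out of the denominator. This part of the objection stands in full: the direction of bias is not established.

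**Follow-up is wider than clinic attendance.** Section 6.1 has public health nurses sending fortnightly wound pictures and has complications recorded. Section 7.1 records major ipsilateral amputation and return to theatre for bleeding. Wound-related readmission at six months is a secondary objective. This stands in part. Nothing forbids a record check, and a diligent team might make one. But none of these provisions is named as a source of 12-month reintervention status for someone who has stopped attending, the pictures are for timing wound healing, and the adverse events listed cover only part of reintervention.

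**Sampling error is larger.** At 43%, the standard error of the difference between arms is √(2 × 0.43 × 0.57/20) = 15.7 points, and the Wilson 95% interval for 17 of 40 is about 29% to 58%. That is fair, and the pilot rate will be imprecise whatever is done. The spread from handling comes on top of that imprecision, is not reflected in the interval, and is largely avoidable at small cost.

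**Conclusion.** The point holds as a gap and a contradiction. The plan has no stated route to 12-month reintervention status for patients who stop attending, no rule for unknown status or death in the primary endpoint, and two sections that disagree on whether patients who miss imaging remain in the analysis.

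Its size depends on losses that the documents do not predict. With 4 of 20 lost and 43% among those observed, handling alone spans 34.4% to 54.4%; with 2 of 20 lost, 38.7% to 48.7%. The 43%, the loss fractions and the 30% relative reduction are all assumptions. If every patient is traced, the spread disappears. It should be corrected before the pilot rate is used for planning.

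**What to change.** - **Section 6.3.** For every randomised patient who has not refused use of their data, establish vital status and any reintervention, with its date, to 12 months. Use theatre and admission records, the GP or public health nurse, or a telephone call, whether or not the patient attends or is imaged.
- **Sections 6.4 and 8.** Reconcile them so that missed imaging is recorded as a deviation but does not remove a patient from the primary analysis.
- **Section 8.** Report the 12-month cumulative incidence of reintervention by arm over all randomised patients, with death as a competing event. Censor only patients of unknown status, at last known contact. Show deaths and losses by arm, and carry this estimate to the power calculation.

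The cost is a wording change, a consent-form line permitting record follow-up, and a few record checks by the existing team among 40 patients. No treatment or visit changes.

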6.4 Protocol Violations

The following will be deemed a protocol violation and the participant will be removed from the trial:

1. Non-adherence to repeat imaging;
2. Withdrawal of consent for procedure or inclusion in study.

	Screening	Enrolment	Intervention	Follow up 6 weeks	Follow op 6 months	Follow up 1 year
Consent		X				
History and Exam	x	X				
Imaging	x		x		x	x
Intervention			x	x	x	x
Clinical follow-up				x	x	x

7. Safety Parameters:

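### Removing participants for missed imaging or a declined procedure (section 6.4) conflicts with intention to treat (section 8) and can lose the 12-month primary outcome

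*Combined protocol and SAP*

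**What the plan says.** Section 6.4 of the combined protocol and SAP gives the removal rule: "The following will be deemed a protocol violation and the participant will be removed from the trial". It has two triggers: "Non-adherence to repeat imaging" and "Withdrawal of consent for procedure or inclusion in study". The second joins two different decisions, declining the operation and leaving the study.

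Section 8 says "All analyses will be performed on an intention to treat basis". It also anticipates departures from allocation: "we expect a small number of patients may ultimately not undergo treatment as initially planned". Losses to follow-up are to be reported, but no method for missing outcomes is given.

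Section 6.3 covers missed imaging as well, with a different response: "any non-attendance to clinic or imaging will be followed up by a member of the team", and "Any reasons not able to attend will be recorded".

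The primary efficacy endpoint in section 3.2.1 is the number of patients per group with "surgical reintervention at twelve months post-operatively". The primary objective in section 2.1 is to gather data good enough for the power calculation of a later randomised trial.

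Imaging appears at three post-operative times: within 48 hours (section 5), at 6 months (section 6.1) and, in the schedule table only, at 1 year. The table also marks clinical follow-up at 1 year.

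**The concern.** A randomised participant who misses an x-ray, or who declines the operation after allocation, is in the analysis under section 8 and out of the trial under section 6.4. The set for the primary analysis therefore depends on which section the trial team follows.

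Reintervention is a clinical event. It can be established at the 1-year visit whether or not a film was taken at 48 hours or 6 months. Removing someone for a missed film discards information on an endpoint that the film does not define.

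Missed imaging may also be related to outcome. A patient who has gone on to a below- or above-knee amputation, for example, may be less likely to attend for a foot x-ray. The remaining patients would then give a distorted reintervention rate, and that rate is what the pilot exists to deliver.

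**Working it through.** **Setting the sections side by side**

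| Event after randomisation | Section 6.4 | Section 6.3 | Section 8 |
|---|---|---|---|
| Missed repeat imaging | Removed | Chased, reason recorded | Analysed by intention to treat |
| Procedure consent withdrawn | Removed | Not addressed | Expected in a few; analysed by intention to treat |
| Study consent withdrawn | Removed | Not addressed | Losses reported |

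Only the last row can properly end data collection. On timing, the 48-hour and 6-month films both precede the 12-month endpoint, so removal for missing either one comes before the primary outcome is known.

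**Illustrating the size**

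The protocol gives no removal rate and no power calculation, so there is no planned figure to reproduce beyond 20 + 20 = 40. What follows rests on assumptions.

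*Event rate.* The background cites 63 of 146 patients with further ipsilateral amputation: 63/146 = 43.2%. This is a stand-in. It counts re-amputation rather than all reinterventions, and no follow-up time is given. Applied to 40 patients, 0.432 × 40 = 17.3, taken as 17 events (17/40 = 42.5%).

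*Bounds with k patients removed and their data not used.* The rate among those left lies between (17 − k)/(40 − k), if all removed had events, and 17/(40 − k), if none had.

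- k = 4: 13/36 = 36.1% to 17/36 = 47.2%.
- k = 8: 9/32 = 28.1% to 17/32 = 53.1%.

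The upper ends also arise if events seen before removal are kept while removed event-free patients leave the denominator.

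*Expected rate by miss rate.* With miss rate a in patients with the event and b in those without, the rate among those kept is 0.432(1 − a) / [0.432(1 − a) + 0.568(1 − b)].

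| a (event) | b (no event) | Rate among those kept |
|---|---|---|
| 10% | 10% | 43.2% |
| 20% | 10% | 40.3% |
| 10% | 20% | 46.1% |

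Equal miss rates cause no expected shift. Unequal ones move the rate in either direction.

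*An extreme case.* If all 21 major amputees in the cited cohort had been removed and their data discarded, the rate would be (63 − 21)/(146 − 21) = 42/125 = 33.6%.

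**Effect on the later trial's sample size**

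Assume a two-sided 5% level, 80% power and pooled variance. Patients per arm:

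| Control rate | One-third relative reduction | 15-point absolute difference |
|---|---|---|
| 43.2% | 174 | 159 |
| 33.6% | 252 | 134 |

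The lower rate raises the requirement on one scale and lowers it on the other, so no direction of error in the future sample size can be claimed.

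**The case against.** The strongest reply is that section 6.4 is about participation and never says that removed patients leave the analysis. Section 8 states intention to treat twice and says outcomes of all patients are recorded. Read together, allocation defines the set and removal merely creates missing outcomes. That reading is possible, but it does not rescue the plan: the 12-month outcome is still lost because of the protocol's own rule, and no handling of it is specified.

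Sections 6.3 and 6.4 might be successive steps, with chasing first and removal only for persistent non-adherence. The text does not say so, nor does it say which or how many missed films trigger removal.

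Several points do stand:

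- Randomisation takes place on the day of surgery (section 4.4), and outpatients are asked for consent again that day (section 4.3.1). Many withdrawals from the procedure will therefore precede randomisation and affect no analysis set.
- A patient randomised but never operated on has no date from which to count twelve post-operative months. The fix has to supply one.
- The lower bounds and the 33.6% case require observed events to be discarded. Section 7.1 says major ipsilateral amputations are recorded and reported, which makes the 33.6% case a strained one. Section 7.1 does not, however, say that removed participants stay in the primary analysis.
- The milder scenarios shift the rate by about 3 points, against a 95% half-width, at an assumed 43%, of 1.96 × √(0.43 × 0.57/40) = 15.3 points pooled and 21.7 points with 20 in one arm. The shift is small beside the pilot's imprecision, but imprecision is reported with the estimate and selection of this kind is not.
- The consent pages were not available for this review. They may contain a rule on data already collected; the protocol sections reviewed contain none.

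**Conclusion.** The point holds. Section 6.4 conflicts with section 8 and sits awkwardly with section 6.3. On either reading of removal, a 12-month outcome that the schedule already provides for can be lost. This should be corrected because it bears on the primary endpoint and on the pilot's primary objective, and outcomes not collected may not be recoverable later.

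The conclusion comes from comparing the sections and needs no assumed figure. Its numerical consequence is unknown in direction and size. The illustrations depend on the borrowed 43.2% rate, on assumed removal numbers and, for the bounds, on data from removed participants not being used. No stated power is lost, because the pilot states none.

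**What to change.** In section 6.4, replace removal with the following:

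- Missed imaging is recorded as a protocol deviation. The participant stays in follow-up to the 1-year visit and in the intention-to-treat set, and 12-month reintervention status is collected with or without films.
- Withdrawal from the procedure does not end follow-up. State the date from which twelve months runs for a participant who was randomised but not operated on.
- Only withdrawal of consent for further data collection ends follow-up, and data collected up to then are kept.

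Apply the same analysis rule to participants whom investigators remove under section 6.2.

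In section 8, report by arm how many participants have unknown 12-month status and why. Show the reintervention rate with all of them counted as events and then as non-events.

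Reconcile the imaging time points in section 5, section 6.1 and the schedule table, so that it is clear which films are required.

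The cost is protocol wording, since reintervention status can be taken at the 1-year clinical follow-up already scheduled. The consent form should be checked to confirm that it permits continued follow-up and retention of data after partial withdrawal.
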